## **7.0 SELECTION AND DISCONTINUATION/WITHDRAWAL OF SUBJECTS**

### **7.1 Inclusion Criteria**

In order to be eligible for participation in this trial, the subject must:

1. Understand the trial procedures and agree to participate by providing written informed consent.
2. Be willing and able to comply with all trial procedures and restrictions.
3. Be a man or woman (with no child bearing potential) aged 18 to 55 years, inclusive, at the Screening Visit.
4. Have a body mass index (BMI)  $\geq 18$  and  $\leq 30 \text{ kg/m}^2$  and a body weight  $>50 \text{ kg}$  at the Screening Visit.
5. Be a nonsmoker who has not used tobacco- or nicotine-containing products (eg, nicotine patch) for at least 6 months before administration of the initial dose of trial drug/invasive procedure.
6. Be judged to be in good health by the investigator, based on clinical evaluations including laboratory safety tests, medical history, physical examination, 12-lead ECG, and vital sign measurements performed at the Screening Visit and before administration of the initial dose of trial drug.
7. Meet the following birth control requirements:
  - Is a male subject\* who is sterile or agrees to use an appropriate method of contraception, including a condom with spermicide, from trial drug administration on the first day of the first dose until 5 half-lives plus 90 days after administration of the last dose of trial drug. No restrictions are required for a vasectomized male subject provided the subject is at least 1 year post-bilateral vasectomy procedure before trial drug administration on the first day of the first dose. A male subject whose vasectomy procedure was performed less than 1 year before trial drug administration on the first day of the first dose must follow the same restrictions as a nonvasectomized man. Appropriate documentation of surgical procedure should be provided.
  - Is a male subject who agrees to not donate sperm from trial drug administration on the first day of the first dose until 5 half-lives plus 90 days after administration of the last dose of trial drug.
  - Is a female subject\* with no childbearing potential, defined by at least 1 of the following criteria:

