### 7.11.4 12-Lead ECGs

The scheduled 12-lead ECG data will be collected according to [Appendix A](#). The ECG parameters include heart rate, PR interval, QRS duration, QT interval, and QT interval with Fredericia's corrections (QTcF).

Quantitative triplicate ECG measurements at each time point will be averaged. Descriptive statistics (N, mean, median, SD, minimum and maximum) of quantitative ECG data will be summarized by regimen for baseline, post-dosing, and change from baseline at each scheduled time point. For each regimen (period), baseline is defined as the last non-missing ECG measurement at or prior to predose (time relative to TAK-906 dosing) in the corresponding period. Only the ECGs collected at the scheduled visits or time points will be included in the summary. No inferential analysis will be performed for the observed ECGs.

For ECG interpretation data, shift table will be provided as the number of subjects to assess interpretation status change from baseline to each scheduled post-baseline measurement by regimen. In the ECG shift table, the best value out of triplicate ECG interpretations will be used to represent baseline evaluation, and the worst value will be used to represent post baseline evaluation.

All individual ECGs that meet Takeda's predefined criteria for markedly abnormal values (Appendix E) will be listed. The number and percentage of subjects with at least 1 markedly abnormal ECG measurement will be summarized by regimen. The mapping of the subjects who meet the MAV criteria will be listed as a table. All post dose ECGs within 7 days of the last dose, including both scheduled and unscheduled measurements, will be included in the MAV summaries.

All ECG data will be presented in the listings. ECG MAVs will be flagged in the listings.

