**Appendix A Schedule of Trial Procedures**

Procedures/Assessments	Screening	Period 1 (a)					Period 2					Follow-up/Early Termination	
	Day -28 to -2	Day					Day					10-14 days after last dose of TAK-906	
		-1	Pre-dose (Day 1)	1	2	3	1	2	3	4	5		6
Administrative Procedures													
Informed consent	X												
Inclusion/exclusion criteria	X	X	X										
Medical history/demographics	X												
Prior and concomitant medication review		-----Continuous Monitoring-----											
Clinic Procedures/Assessments													
Full physical examination	X	X (b)										X	
Height	X												
Weight	X												
BMI	X												
12-Lead ECG	X		X(c)	X(c)	X				X(c)		X	X	
Semirecumbent vital signs (heart rate [HR], systolic blood pressure and diastolic blood pressure)	X		X(d)	X(d)	X		X		X(d)		X	X	
Vital signs (respiratory rate, oral [at the floor of the mouth]/tympanic temperature) rate	X		X	X	X		X		X		X	X	
TAK-906 administration				X					X				
Itraconazole administration (e)							X	X	X	X	X		
AE monitoring		-----Continuous Monitoring-----											
Laboratory Procedures/Assessments													
Hematology	X	X (b)					X (b)					X	X
Urinalysis	X	X (b)					X (b)					X	X
Chemistry	X	X (b)					X (b)					X	X
Serum follicle stimulating hormone (FSH)	X												
β-human chorionic gonadotropin (hCG)	X	X											X

Procedures/Assessments	Screening	Period 1 (a)					Period 2					Follow-up/Early Termination
	Day -28 to -2	-1	Pre-dose (Day 1)	Day			Day					10-14 days after last dose of TAK-906
				1	2	3	1	2	3	4	5	
Urine drug screen	X	X				X						
Urine alcohol test/alcohol breath test (f)	X	X				X						
Hepatitis screen	X											
Human immunodeficiency virus (HIV)	X											
Pharmacokinetics Evaluations												
CCI												
CCI												
Pharmacogenomic (PGx) Evaluations												
PGx DNA collection			X									
PGx RNA collection			X									
Other												
Confinement			X-----X					X-----X				
Meals fasting (i)				X					X	X		

- (a) There will be a minimum 4 day washout between Periods 1 and 2, starting from administration of TAK-906 maleate on Day 1 of Period 1.
- (b) Day 1 predose assessment may be done within approximately 24 hours prior to trial drug administration.
- (c) Triplicate measurements to be conducted at 0 (predose), 1, 2, 4, 8 and 48 hours postdose (times relative to TAK-906 maleate dose).

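### The ECG interpretation shift table takes the best of three readings at baseline and the worst of three afterwards, so on a normal/abnormal scale with complete triplicates it is expected to show net worsening equal to the triplicate disagreement rate even without a drug or time effect

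*SAP*

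**What the plan says.** SAP 7.11.4 plans a shift table of subject counts "to assess interpretation status change from baseline to each scheduled post-baseline measurement by regimen". To reduce each triplicate to one value, "the best value out of triplicate ECG interpretations will be used to represent baseline evaluation, and the worst value will be used" for the post-baseline evaluation. SAP Appendix A, footnote (c), gives the schedule: "Triplicate measurements to be conducted at 0 (predose), 1, 2, 4, 8 and 48 hours postdose", timed from the TAK-906 dose. The Follow-up ECG does not carry that footnote.

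Other parts of the same section limit the scope:
- Measured ECG intervals follow one rule on both sides: "Quantitative triplicate ECG measurements at each time point will be averaged".
- Each period has its own reference: "baseline is defined as the last non-missing ECG measurement at or prior to predose" in that period.
- The markedly abnormal value (MAV) summary has no best/worst selection: "The number and percentage of subjects with at least 1 markedly abnormal ECG measurement will be summarized by regimen".
- "No inferential analysis will be performed for the observed ECGs".

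Protocol 11.1.4.4 plans shift tables of the investigator's ECG interpretations against Baseline and is silent on how a triplicate is reduced to one value. Neither document lists the interpretation categories or gives a rate of abnormal readings or of agreement within a triplicate.

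**The concern.** A shift table should show about as many improvements as deteriorations when nothing has changed. Here a subject counts as abnormal at baseline only if all three readings are abnormal, but as abnormal after dosing if any one reading is. Mixed triplicates are therefore read as normal before dosing and as abnormal after it, so ordinary reading-to-reading variation appears as deterioration and almost never as improvement. A reader of one regimen's counts cannot tell from the table how many normal-to-abnormal shifts come from the rule, and the SAP does not say that net worsening is expected without a drug effect. With about 12 subjects, one or two such shifts at a time point would be noticed. Safety and tolerability with and without the inhibitor is the secondary objective, and this is the only planned summary of the investigator's ECG interpretations.

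**Working it through.** The plan states no figure on this point, so there is none to reproduce.

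**Inputs from the documents.** Three readings at predose and at each of 1, 2, 4, 8 and 48 hours (SAP Appendix A, footnote c); best at baseline and worst afterwards (SAP 7.11.4); about 12 subjects (SAP 6.0).

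**Assumptions.** Two categories. The readings of a subject are exchangeable, with the same distribution before and after dosing. p is the chance that a reading is abnormal, and ICC is the correlation between readings of one subject. The values of p and ICC are assumed.

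**Identity.** Let A be the event that all three baseline readings are abnormal, and B the event that at least one post-baseline reading is abnormal.

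Worsening − improvement = P(not A, B) − P(A, not B) = P(B) − P(A).

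Without a drug or time effect, P(B) − P(A) = P(1, 2 or 3 of 3 abnormal) − P(3 of 3 abnormal) = P(1 or 2 of 3 abnormal). This is the disagreement rate, and it equals 3p(1−p)(1−ICC). It is zero only if triplicates always agree.

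- p = 2%, ICC = 1/1.1 = 0.91: 3 × 0.02 × 0.98 × 0.0909 = 0.535%. Worsening is 0.541% and improvement 0.006%.
- p = 10%, independent: 3 × 0.10 × 0.90 = 27.0%. Worsening is (1 − 0.1³)(1 − 0.9³) = 27.073% and improvement 0.1³ × 0.9³ = 0.073%.

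**Range.** Worsening per time point without any effect, from exact beta-binomial sums in which a subject's readings share a probability drawn from Beta(pc, (1−p)c), ICC = 1/(1+c), c = 0.1, 0.5, 2, 5:

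| p | ICC 0.91 | 0.67 | 0.33 | 0.17 | independent |
|---|---|---|---|---|---|
| 2% | 0.54% | 1.98% | 3.96% | 4.93% | 5.88% |
| 5% | 1.31% | 4.8% | 9.6% | 12.0% | 14.3% |
| 10% | 2.48% | 9.1% | 18.2% | 22.7% | 27.1% |

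Improvement is about 0.2% or less throughout. Multiplied by 12, this is 0.06 to 3.2 subjects per time point. Over 12 × 5 = 60 entries per regimen it is 0.3 to 16.2.

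**Not every disagreement changes a cell.** Six two-level readings give 2⁶ = 64 patterns. Four are unanimous on both sides, leaving 60 with a disagreement. Worsening occurs in 7 × 7 = 49 patterns, of which 48 contain a disagreement. The one improving pattern contains none. So of the 60, 48 show worsening, 12 no change and none improvement; 21 fall in the same cell as the middle reading would give. These are unweighted counts, not probabilities.

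**More than two categories.** For three ordered categories with independent readings, the net proportion worsening against the disagreement rate is 0.383 vs 0.383 (85/14/1%), 0.634 vs 0.641 (70/25/5%) and 0.840 vs 0.889 (equal thirds). The largest gap in a random search was about 0.05, always below the disagreement rate.

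**Single later reading.** If a visit such as Follow-up has one reading against a best-of-three baseline, the net is smaller: 0.26% (p = 2%, ICC 0.91) to 9.9% (p = 10%, independent: 0.1 − 0.1³ = 0.099).

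**Middle reading on both sides, complete triplicates.** Over the same grid, worsening and improvement are each 0.1% to 4.1% (0.07 to 2.5 of 60 entries), with an expected net of zero.

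**The case against.** The rule is openly stated and defensible. In a small safety data set it makes a single abnormal post-dose tracing visible as a shift. The table is descriptive and no decision in the documents depends on it. All ECG data are to be listed, so a reader with the listings can check the triplicate behind any shift. The subjects are screened as healthy partly on "12-lead ECG, and vital sign measurements performed at the Screening Visit and before administration of the initial dose of trial drug", so low abnormal rates are plausible, and the top corner of the table (10% abnormal, independent repeat readings of one person) is hard to credit.

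All of this stands, and it keeps the point small. It does not remove the bias within a regimen: the direction is fixed unless agreement is perfect, and the table carries no warning.

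A reader might go further and infer that the rule exaggerates the effect of itraconazole. The documents do not support that: both regimens use the same rule with a period-specific baseline, so the excess cancels in expectation when disagreement rates are equal. A reader might also infer a departure from the protocol, but the protocol sets no rule for reducing triplicates that could be departed from.

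**Conclusion.** The point holds and is minor. For two categories, complete triplicates on both sides and no drug or time effect, the expected net worsening equals the triplicate disagreement rate exactly. With more ordered categories it is at or somewhat below that rate, and with fewer post-baseline than baseline readings it is smaller. The size cannot be fixed from the documents: 0.5% to 27% per time point is what the assumed rates give, and the true figure may be near zero. It should not be read as an estimate for this trial, nor as a bias in the ECG safety analysis as a whole. Averaged intervals, MAV summaries, listings and the primary PK analysis are untouched.

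**What to change.** Keep the existing table, label it, and add one symmetric table. Suggested text for SAP 7.11.4:

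> *The shift table based on the best baseline and worst post-baseline interpretation will be labelled as a worst-case display that is expected to show net worsening without any drug effect. A second shift table will use the middle of the three interpretations, ordered from normal to most abnormal, at baseline and at each post-baseline time point. It will include only entries with three interpretations on both sides; the number of excluded entries will be shown, and these remain in the worst-case table and the listings.*

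The restriction matters. A fallback such as taking the worse of two readings, or a lone reading, when a triplicate is incomplete would bring a bias back, and its sign would depend on which side is short. At p = 10% with independent readings, the middle of three is abnormal with probability 3 × 0.01 × 0.9 + 0.001 = 2.8%, the worse of two with 1 − 0.9² = 19%, and a single reading with 10%. Three baseline readings against two post-baseline would give +16.2%. Two against three would give −16.2% and one against three −7.2%, which could hide worsening.

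The cost is a few SAP sentences, one extra descriptive table and its program, from data already collected. On its own the symmetric table would not show a single abnormal post-dose tracing as a shift, which is why the labelled worst-case table stays.

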#### **7.11.5 Other Observations Related to Safety**

Physical examination findings and all cases of overdose will be presented in data listings. No summary tables will be provided.

#### **7.12 Interim Analysis**

Not applicable.

#### **7.13 Changes in the Statistical Analysis Plan**

None.

**Appendix A Schedule of Trial Procedures**

Procedures/Assessments	Screening	Period 1 (a)					Period 2					Follow-up/Early Termination	
	Day -28 to -2	Day					Day					10-14 days after last dose of TAK-906	
		-1	Pre-dose (Day 1)	1	2	3	1	2	3	4	5		6
Administrative Procedures													
Informed consent	X												
Inclusion/exclusion criteria	X	X	X										
Medical history/demographics	X												
Prior and concomitant medication review		-----Continuous Monitoring-----											
Clinic Procedures/Assessments													
Full physical examination	X	X (b)										X	
Height	X												
Weight	X												
BMI	X												
12-Lead ECG	X		X(c)	X(c)	X				X(c)		X	X	
Semirecumbent vital signs (heart rate [HR], systolic blood pressure and diastolic blood pressure)	X		X(d)	X(d)	X		X		X(d)		X	X	
Vital signs (respiratory rate, oral [at the floor of the mouth]/tympanic temperature) rate	X		X	X	X		X		X		X	X	
TAK-906 administration				X					X				
Itraconazole administration (e)							X	X	X	X	X		
AE monitoring		-----Continuous Monitoring-----											
Laboratory Procedures/Assessments													
Hematology	X	X (b)					X (b)					X	X
Urinalysis	X	X (b)					X (b)					X	X
Chemistry	X	X (b)					X (b)					X	X
Serum follicle stimulating hormone (FSH)	X												
β-human chorionic gonadotropin (hCG)	X	X											X

Procedures/Assessments	Screening	Period 1 (a)					Period 2					Follow-up/Early Termination
	Day -28 to -2	-1	Pre-dose (Day 1)	Day			Day					10-14 days after last dose of TAK-906
				1	2	3	1	2	3	4	5	
Urine drug screen	X	X				X						
Urine alcohol test/alcohol breath test (f)	X	X				X						
Hepatitis screen	X											
Human immunodeficiency virus (HIV)	X											
Pharmacokinetics Evaluations												
CCI												
CCI												
Pharmacogenomic (PGx) Evaluations												
PGx DNA collection			X									
PGx RNA collection			X									
Other												
Confinement			X-----X					X-----X				
Meals fasting (i)				X					X	X		

- (a) There will be a minimum 4 day washout between Periods 1 and 2, starting from administration of TAK-906 maleate on Day 1 of Period 1.
- (b) Day 1 predose assessment may be done within approximately 24 hours prior to trial drug administration.
- (c) Triplicate measurements to be conducted at 0 (predose), 1, 2, 4, 8 and 48 hours postdose (times relative to TAK-906 maleate dose).
- (d) Measured at 0 (predose), 1, 2, 4, 8 and 48 hours postdose (times relative to TAK-906 maleate dose).
- (e) Itraconazole will be administered once daily at the same time each day and 1 hour prior to TAK-906 maleate on Day 4.
- (f) An alcohol breath test may be performed at the discretion of the investigator.
- (g) CCI
- CCI
- (h) CCI
- CCI
- (i) Subjects will fast overnight at least 8 hour before dose of TAK-906 maleate on Day 1 of Period 1 and at least 8 hours before itraconazole and TAK-906 maleate doses on Day 4 of Period 2.

## Appendix B Clinical Laboratory Tests and Screening

### Chemistry

Albumin	Alkaline phosphatase
ALT	AST
Blood urea nitrogen	Calcium
Carbon dioxide	Chloride
Creatinine	Glucose
Gamma-glutamyl transferase	Sodium
Potassium	Bilirubin (total), if above ULN, will be fractionated
Protein (total)	

### Hematology

Erythrocytes (red blood cells [RBCs])	Hemoglobin
Hematocrit	Platelets
Leukocytes (white blood cells [WBCs]) with absolute differential	

### Urinalysis

Protein	Glucose
Blood	Nitrite

Urine microscopy will be performed if urinalysis is abnormal. Microscopy consists of RBC/high-power field, WBC/high-power field, and casts.

### Urine Drug Screen

Amphetamines	3,4-methylenedioxy-methamphetamine
Barbiturates	Methadone/metabolite
Benzodiazepines	Opiates
Buprenorphine/metabolite	Oxycodone/oxymorphone
Cannabinoids	Phencyclidine
Cocaine/metabolites	Cotinine

### Alcohol Screen

Subjects will undergo a urine alcohol test. An alcohol breath test may be performed at the discretion of the investigator.

### Screening - Serum

β-human chorionic gonadotropin (women only)	FSH (women only).
HIV test	Hepatitis panel, including hepatitis B surface antigen and anti-hepatitis C virus.

## Appendix C Criteria for Identification of Markedly Abnormal Laboratory Values

### *Hematology—Criteria for Markedly Abnormal Values*

Parameter	Unit	Low Abnormal	High Abnormal
Hemoglobin	Both	<0.8 × LLN	>1.2 × ULN
Hematocrit	Both	<0.8 × LLN	>1.2 × ULN
RBC count	Both	<0.8 × LLN	>1.2 × ULN
WBC count	Both	<0.5 x LLN	>1.5 x ULN
Platelet count	Conventional SI	<75 x 10  /μL <75 x 10  /L	>600 x 10  /μL >600 x 10  /L

LLN=lower limit of normal, RBC=red blood cell, ULN=upper limit of normal, WBC=white blood cell.

### *Serum Chemistry—Criteria for Markedly Abnormal Values*

Parameter	Unit	Low Abnormal	High Abnormal
ALT	Both	--	>3x ULN
AST	Both	--	>3x ULN
GGT	Both	--	>3x ULN
Alkaline phosphatase	Both	--	>3x ULN
Total bilirubin	Conventional SI	-- --	>2.0 mg/dL >34.2 μmol/L
Albumin	Conventional SI	<2.5 g/dL <25 g/L	-- --
Total protein	Both	<0.8x LLN	>1.2x ULN
Creatinine	Conventional SI	--	>2.0 mg/dL >177 μmol/L
Blood urea nitrogen	Conventional SI		>30 mg/dL >10.7 mmol/L
Sodium	Conventional SI	<130 mEq/L <130 mmol/L	>150 mEq/L >150 mmol/L
Potassium	Conventional SI	<3.0 mEq/L <3.0 mmol/L	>6.0 mEq/L >6.0 mmol/L
Glucose	Conventional SI	<50 mg/dL <2.8 mmol/L	>350 mg/dL >19.4 mmol/L
Chloride	Conventional SI	<75 mEq/L <75 mmol/L	>126 mEq/L >126 mmol/L
Calcium	Conventional SI	<7.0 mg/dL <1.75 mmol/L	>11.5 mg/dL >2.88 mmol/L
Carbon dioxide	Conventional SI	<8.0 mEq/L <8.0 mmol/L	

ALT=alanine aminotransferase, AST=aspartate aminotransferase, GGT=γ-glutamyl transferase, LLN=lower limit of normal, ULN=upper limit of normal.

**Appendix D Criteria for Abnormal Changes from Baseline of Vital Signs**

Parameter	Unit	Lower Criteria	Upper Criteria
Pulse	bpm	<50	>120
Systolic blood pressure	mm Hg	<85	>180
Diastolic blood pressure	mm Hg	<50	>110
Body temperature	°C	<35.6	>37.7

**Appendix E Criteria for Markedly Abnormal Values for the 12-Lead ECG Parameters**

Parameter	Lower Criteria	Upper Criteria
Heart rate	<50 beats per minute	>120 beats per minute
PR	≤120 milliseconds	≥200 milliseconds
QT Interval	≤300 milliseconds	≥460 milliseconds
QTcF Interval	≤300 milliseconds	≥500 milliseconds OR ≥30 milliseconds change from baseline and ≥450 milliseconds
QRS	≤60 milliseconds	≥120 milliseconds

ELECTRONIC SIGNATURES

Signed by	Meaning of Signature	Server Date (dd-MMM-yyyy HH:mm 'UTC')
PPD	Pharmacovigilance Approval	07-Aug-2017 13:57 UTC
	Clinical Pharmacology Approval	07-Aug-2017 14:00 UTC
	Clinical Approval	07-Aug-2017 14:05 UTC
	Statistical Approval	07-Aug-2017 14:05 UTC
	Statistical Approval	07-Aug-2017 19:20 UTC
